5.2. Analysis Populations

The following subject populations (ie, analysis sets) will be evaluated and used for presentation of the data:

1. Full Analysis Set (FAS)
2. Safety Analysis Set (SAS)

3. Dose Determining Set (DDS)
4. Evaluable Analysis Set (EAS)

5.2.1. Full Analysis Set

Full Analysis Set (FAS): All subjects who received at least one dose of study treatment. The FAS is the primary analysis population for efficacy and will be the default analysis set for all analyses in each phase of study, unless otherwise specified. Subjects will be analyzed according to the treatment assigned.

5.2.2. Safety Analysis Set

Safety Analysis Set (SAS): All subjects who received at least 1 dose of study treatment. Subjects will be classified according to the treatment received, where treatment received is defined as the assigned dose level/schedule if it was received at least once, or the first dose level/schedule received if assigned treatment was never received. The SAS will be the primary set for the analysis of safety data in each phase of study.

5.2.3. Dose Determining Set

Dose Determining Set (DDS): All subjects who take at least one dose of study drug in the dose escalation phase and either had a DLT during Cycle 1, regardless of amount of study drug exposure, or have no DLT and completed at least 75% of their planned Cycle 1 doses (21 out of 28 days), and were considered by the Clinical Study Team to have had sufficient safety data available to conclude that a DLT did not occur during Cycle 1.

The DDS will be the default analysis set for the dose escalation phase for all MTD related analyses. Subjects will be analyzed according to the assigned dose group.

5.2.4. Evaluable Analysis Set

Evaluable Analysis Set (EAS): All subjects in the FAS for whom the baseline efficacy parameters (eg, hematologic and bone marrow assessments) and at least 1 post baseline response assessment at Day 28 or later are available and evaluable and who have experienced no major protocol violations. Sensitivity efficacy analyses will be produced using the EAS, if applicable. Subjects will be analyzed according to the assigned dose group. Major protocol violations leading to exclusion from EAS are defined as any of the following:

- Subject does not have an advanced hematologic malignancy.
- Subject does not have documented IDH2 gene-mutated disease.
- Subject received concomitant treatment for their malignancy other than AG-221.

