### 8.3. Exclusion Criteria

Subjects who meet any of the following criteria will not be enrolled in the study:

1. Subjects who have undergone a hematopoietic stem cell transplant (HSCT) within 60 days of the first dose of AG-221, or subjects on immunosuppressive therapy post HSCT at the time of screening, or with clinically significant graft-versus-host disease (GVHD). (The use of a stable dose of oral steroids post HSCT and/or topical steroids for ongoing skin GVHD is permitted with Medical Monitor approval.)
2. Subjects who received systemic anticancer therapy or radiotherapy <14 days prior to their first day of study drug administration. (Hydroxyurea is allowed prior to enrollment and after the start of AG-221 for the control of peripheral leukemic blasts in subjects with leukocytosis (white blood cell [WBC] counts >30,000/ $\mu$ L).
3. Subjects who received a small molecule investigational agent <14 days prior to their first day of study drug administration. In addition, the first dose of AG-221 should not occur before a period  $\geq$ 5 half-lives of the investigational agent has elapsed.
4. Subjects taking the following sensitive CYP substrate medications that have a narrow therapeutic range are excluded from the study unless they can be transferred to other medications within  $\geq$ 5 half-lives prior to dosing: paclitaxel (CYP2C8) warfarin, phenytoin (CYP2C9), S-mephenytoin (CYP2C19), thioridazine (CYP2D6), theophylline and tizanidine (CYP1A2).

5. Subjects taking the P-gp and BCRP transporter-sensitive substrates digoxin and rosuvastatin should be excluded from the study unless they can be transferred to other medications within  $\geq 5$  half-lives prior to dosing.
6. Subjects for whom potentially curative anticancer therapy is available.
7. Subjects who are pregnant or lactating.
8. Subjects with an active severe infection that required anti-infective therapy or with an unexplained fever  $>38.5^{\circ}\text{C}$  during screening visits or on their first day of study drug administration (at the discretion of the Investigator, subjects with tumor fever may be enrolled).
9. Subjects with known hypersensitivity to any of the components of AG-221.
10. Subjects with New York Heart Association (NYHA) Class III or IV congestive heart failure or LVEF  $<40\%$  by echocardiogram (ECHO) or multi-gated acquisition (MUGA) scan obtained within approximately 28 days of C1D1.

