### **9.8.3. Leukocytosis**

Initiation of treatment with the differentiating agents may lead to rapid WBC expansion not associated with infectious process and not manifesting with the signs and symptoms of IDH Differentiation Syndrome discussed above.

In subjects with elevated WBC, prompt initiation of hydroxyurea is suggested, as per standard local practices (eg, dose of 2 to 3 g PO twice or 3 times daily for  $WBC > 30 \times 10^9/L$ ). In case of severe leukocytosis ( $WBC > 100 \times 10^9/L$ ), use of leukapheresis may be appropriate. Subject should be regularly monitored for changes in WBC count and for new signs and symptoms of infection or IDH Differentiation Syndrome.

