## 12.2. Populations for Analysis

The following subject populations (i.e., analysis sets) will be evaluated and used for presentation of the data:

- Full Analysis Set (FAS): All subjects who were enrolled and received at least one dose of study treatment. Subjects will be classified according to the assigned dose level and schedule. The FAS is the primary analysis population for efficacy and will be the default analysis set for all analyses, unless otherwise specified.
- Dose Determining Set (DDS): All dose escalation subjects who either had a DLT during Cycle 1, or who completed at least 75% of their planned Cycle 1 doses (21 out of 28 days) and were considered by the Clinical Study Team to have had sufficient safety data available to conclude that a DLT did not occur during Cycle 1.
- Safety Analysis Set (SAS): All subjects who were enrolled and received at least one dose of study treatment. Subjects will be classified according to the treatment received, where treatment received is defined as the assigned dose level/schedule if it was received at least once, or the first dose level/schedule received if assigned treatment was never received. The SAS will be the primary set for the analysis of safety data.
- Evaluable Analysis Sets
  - Evaluable Analysis Set (EAS): All subjects in the FAS for whom the baseline response assessment and at least one post baseline response assessment at Day 28 or later are available and evaluable.
  - Central Evaluable Analysis Set (CEAS): All subjects in the FAS for whom the baseline response assessment and at least one post baseline response assessment at Day 28 or later are available and evaluable by central independent review.

Results of the potential clinical activity of AG-221 will be primarily based on the FAS. Additional efficacy analyses will be produced for the EAS and CEAS.

- Pharmacokinetic Analysis Set (PAS): All subjects who have at least one blood sample providing evaluable PK data for AG-221.

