10.2. Analysis of Primary Efficacy Endpoint

The primary efficacy endpoint of ORR is defined as the rate of responses including CR, CRi, CRp, PR, mCR (for MDS) and MLFS (for AML) by investigator assessment. The ORR will be summarized by the percentage of responses primarily in the FAS with 2-sided exact binomial 95% CI.

Response will also be summarized by the best objective response following the hierarchical order of CR, CRi/CRp, PR, mCR/MLFS, stable disease, relapse/progressive disease/failure, and not evaluable (NE).

An observed ORR in the pivotal Phase 2 R/R AML FAS subjects with the lower bound of the exact binomial 95% CI greater than 25% is deemed clinically meaningful and exceeds the expected ORR with other available therapies. This will be considered as evidence of clinically significant activity of AG-221. The analyses in the combined Phase 1/2 R/R AML on total daily dose of 100mg utilize larger population and thus provide robust estimate of ORR to better describe the clinical activity of AG-221.

To assess the robustness of the primary analysis, the following sensitivity analyses will be performed:

- (1) ORR in the EAS for the combined Phase 1, Phase 2, and the combined Phase 1/2;

- (2) The ORR assessed by Independent Response Adjudication Committee (IRAC) in the FAS for Phase 1, Phase 2, and the combined Phase 1/2 R/R AML.

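### SAP 5.2.4 does not exempt protocol-permitted hydroxyurea from its concomitant-treatment exclusion, so the EAS sensitivity analyses can be biased, in a direction the documents do not settle

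*SAP*

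**What the plan says.** SAP 5.2.4 admits to the EAS subjects with evaluable baseline efficacy data for whom "at least 1 post baseline response assessment at Day 28 or later are available and evaluable and who have experienced no major protocol violations". It then states: "Major protocol violations leading to exclusion from EAS are defined as any of the following". The third item on that list is "Subject received concomitant treatment for their malignancy other than AG-221". No drug is exempted.

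The protocol allows one such drug. Within the exclusion criterion on systemic anticancer therapy, Protocol 8.3 says: "Hydroxyurea is allowed prior to enrollment and after the start of AG-221 for the control of peripheral leukemic blasts". Protocol 9.8.3 goes further: "In subjects with elevated WBC, prompt initiation of hydroxyurea is suggested". SAP 11.2 expects on-treatment use, because its risk-factor tables include a category for hydroxyurea that carried on past the first dose.

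Protocol 12.2 defines the EAS only by an evaluable baseline assessment and the condition that "at least one post baseline response assessment at Day 28 or later are available and evaluable". It has no violation-based exclusion. SAP Section 13 lists three changes from the protocol (a data cut-off, terminology, and added secondary endpoints), and the new EAS exclusions are not among them.

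SAP 10.2 introduces the EAS analysis of ORR with "To assess the robustness of the primary analysis, the following sensitivity analyses will be performed" and lists it first. SAP 10.3.1.1 and 10.3.1.3 use the EAS in the same way for CRR and CR/CRi/CRp.

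**The concern.** A drug given to control leukemic blasts falls within treatment for the malignancy on the plain meaning of the words. Followed literally, the bullet turns permitted use into a major violation. Two programmers could build two different EAS populations from the same text.

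The exclusion also acts on something that happens after treatment starts and may be related to outcome. A subject given another anti-leukemic drug while on AG-221 is plausibly failing AG-221, and the bullet removes that subject from the denominator. Protocol 12.3, by contrast, keeps subjects whose best response is unknown or not evaluable and counts them as non-responders.

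At stake is whether agreement or disagreement between the EAS and the FAS says anything about robustness. If membership is uncertain and selection depends on post-baseline events, it says little.

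**Working it through.** **Inputs.** Phase 2 N = 125 and a threshold of 42 responses (Protocol 12.1). Two-sided exact 95% interval and a lower bound above 25%, applied to the Phase 2 R/R AML FAS (SAP 10.2). The documents give neither the number of subjects the bullet would remove nor their response rate, so those counts are assumptions shown over a range.

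**Formula.** For x responders in n, the exact limits are: lower = Beta quantile(0.025; x, n − x + 1), upper = Beta quantile(0.975; x + 1, n − x).

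**Step 1: the plan's own figure.** 42/125 = 33.6% (25.4%, 42.6%), as stated. 41/125 = 32.8% (24.7%, 41.8%), so 42 is the smallest count that meets the criterion.

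**Step 2: hydroxyurea users removed.** If h users include r responders, the EAS ORR is (42 − r)/(125 − h). This exceeds 33.6% only when r/h is below 42/125.

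| Assumed h | Assumed r | EAS ORR | 95% CI |
|---|---|---|---|
| 12 | 0 | 42/113 = 37.2% | 28.3%, 46.8% |
| 12 | 7 | 35/113 = 31.0% | 22.6%, 40.4% |
| 25 | 0 | 42/100 = 42.0% | 32.2%, 52.3% |
| 25 | 5 | 37/100 = 37.0% | 27.6%, 47.2% |
| 25 | 8 | 34/100 = 34.0% | 24.8%, 44.2% |
| 25 | 11 | 31/100 = 31.0% | 22.1%, 41.0% |
| 25 | 15 | 27/100 = 27.0% | 18.6%, 36.8% |

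With h = 25 the sign changes between 8 and 9 responders, since 25 × 0.336 = 8.4.

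**Step 3: only non-responders removed.** This is the limiting case for subjects given other anti-leukemic drugs during AG-221. From 42/125, removing 5, 10 or 20 gives 42/120 = 35.0% (26.5%, 44.2%), 42/115 = 36.5% (27.7%, 46.0%) or 42/105 = 40.0% (30.6%, 50.0%).

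Under the same assumption, an FAS result that misses 25% can be paired with an EAS lower bound above it:

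| FAS result | FAS lower bound | Smallest number of non-responders removed |
|---|---|---|
| 41/125 | 24.7% | 2 |
| 40/125 | 23.9% | 6 (40/119, lower bound 25.2%) |
| 38/125 | 22.5% | 12 (38/113, lower bound 25.01%) |
| 36/125 | 21.1% | 19 |

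**The case against.** The strongest reply is that the bullet sits in a list of protocol violations, and use the protocol permits is not naturally a violation. SAP 11.2 treats continued hydroxyurea as expected, SAP Section 7 has a physician assess violations before database lock, and the concomitant-medication sections (Protocol 9.12, parts of SAP 8.4) are redacted and may contain the exemption. This stands as far as it goes: removal of hydroxyurea users is the literal reading, not a stated intention. It does not remove the problem, because SAP 5.2.4 says violations are defined by its bullets and the visible text names no exception.

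A reader might also infer three stronger claims that the documents do not support.

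- *That the exclusion biases the EAS upward.* For hydroxyurea users this is unproven. Protocol 9.8.3 says differentiating agents can cause rapid white-cell expansion, and Protocol 10.8.3 says response can follow an initial rise in blasts. Users could include many responders, and Step 2 shows that this decides the sign. Removing subjects on other active drugs could also remove responses not due to AG-221.
- *That the bullet generally drops treatment failures.* Early failures leave mainly through the Day 28 assessment condition, which is already in Protocol 12.2. The bullet concerns concomitant treatment. Subjects who stop AG-221 and then start something else are not clearly caught, and the SAP handles later therapy separately (8.4.3, Table 3).
- *That the EAS could rescue a failed primary result.* SAP 10.2 ties the 25% criterion to the FAS, and SAP Section 10 calls the EAS supportive. The Step 3 pairings show how the EAS could mislead; they are not a route to meeting the criterion.

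**Conclusion.** The point holds as a defect in the definition of a supportive analysis set. The bullet has no exemption for a drug the protocol permits and suggests, it selects on a post-baseline event, and the violation-based exclusions depart from Protocol 12.2 without being declared.

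The EAS estimates of ORR, CRR and CR/CRi/CRp can therefore be biased. For hydroxyurea users the direction cannot be determined from the documents: with 25 assumed users and 42/125 in the FAS, the EAS ORR could lie anywhere from 27.0% to 42.0% over the 0 to 15 responders examined. For subjects given other anti-leukemic drugs while on AG-221 the bias is plausibly upward, by 2.9 percentage points (36.5% − 33.6%) if 10 are removed and none responded. All these sizes rest on assumed counts.

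The primary FAS ORR, its 25% criterion and the IRAC-assessed ORR in the FAS do not change.

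**What to change.** 1. Amend the third bullet of SAP 5.2.4 so that hydroxyurea use permitted by the protocol does not exclude a subject from the EAS.
2. For subjects given other anti-leukemic therapy during AG-221, preferably keep them in the EAS, count only responses documented before that therapy, and otherwise score them as non-responders. SAP Table 3 already handles subsequent therapy for duration of response by a date rule instead of deleting subjects.
3. List the violation-based EAS exclusions in SAP Section 13 as a change from Protocol 12.2. Deleting the third bullet alone would not restore the protocol's EAS, because the requirement of no major violations and the other two bullets would remain.
4. Add response status by exclusion criterion to the listing of EAS exclusions already planned in SAP Section 7, so that a reader can see the direction of any selection.

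The cost is a short SAP edit, minor reprogramming and a possibly less favourable EAS estimate. The Day 28 condition stays, so the EAS will still differ from the FAS and should be read as supportive.

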6. SUBJECT DISPOSITION

The number of subjects treated, discontinued from treatment and study, along with the primary reason for discontinuation, will be summarized using frequency and percentage.

A summary of subject disposition will be presented separately for Phase 1 Dose Escalation by total daily dose, Part 1 Expansion by cohorts, and Phase 2 R/R AML, as described in items 1, 2, and 4 of [Section 5.1](#), and for the FAS analysis set.

Disposition will also be analyzed for Phase 1 Dose Escalation by assigned dose group and overall for DDS.

Subject disposition for the combined Phase 1 will be presented by malignancy type for overall subjects and by <100 mg, 100 mg, and >100 mg for R/R AML as described in item 3 of [Section 5.1](#) for the FAS analysis set.

Subject disposition for the combined Phase 1/2 will be presented by malignancy type for overall subjects and by <100 mg, 100 mg, and >100 mg and further by relapse/refractory status for R/R AML for the FAS analysis set.

Subjects screened and subjects treated by site will be summarized as described in items 1, 2, and 4 of [Section 5.1](#). A separate summary tabulation will be presented by number of subjects and the reason of screen failures for Phase 1 and Phase 2.

A by-subject data listing will be provided for subjects with reasons for screening failure. Reasons for treatment discontinuation have been collected on the electronic case report form (eCRF) and will be summarized with the following categories:

- Withdrawal of consent
- Due to AE or DLT
- Any medical condition which, in the opinion of the Investigators, would put the subject at risk for continuing treatment
- Experiences disease progression
- Development of an intercurrent medical condition or need for concomitant treatment that precludes further participation in the trial
- The Investigator removes the subject from the trial in the best interests of the subject
- Subject requires use of a prohibited concomitant medication
- Protocol violation: non-adherence to study drug regimen or protocol requirements
- Lost to follow-up
- Pregnancy
- Death
- Bone Marrow Transplant
- Other

Reasons for not completing the study follow-up/study (ie, no more follow-up visits and no longer participating in the study) have been collected on the eCRF and will be summarized for all subjects with the following categories:

- Withdrawal of consent
- Lost to follow-up
- Death
- Other

Listings will be provided for discontinued subjects with reasons for treatment and study discontinuation displayed.

7. **PROTOCOL DEVIATIONS/VIOLATIONS**

Protocol deviations/violations were identified and assessed by the clinical research physician or designee following company standard operational procedure.

Protocol deviations and violations will be reviewed and finalized prior to database lock.

Protocol deviations and violations will be summarized separately for FAS using frequency tabulations and will be presented by subject groups as described in items 1, 2, and 4 of [Section 5.1](#). Unlike other analyses, protocol deviations and violations analyses will be summarized for all subjects in Phase 2. Protocol deviations and violations will also be summarized for the combined Phase 1/2 R/R AML subjects following item 5 in [Section 5.1](#).

A by-subject listing of all subjects with protocol deviations/violations will be provided. A separate listing of subjects with major protocol violations that lead to exclusion from the EAS will be provided.

8. DEMOGRAPHICS AND BASELINE CHARACTERISTICS

Unless specified otherwise, demographics and baseline disease characteristics will be summarized for Phase 1 dose escalation, Part 1 Expansion, and Phase 2 by subject groups as described in items 1, 2, and 4 of [Section 5.1](#) for FAS. Phase 2 R/R AML subjects will be analyzed in EAS as well.

The Phase 1 dose escalation data will also be summarized by assigned dose groups in the DDS.

The combined Phase 1 and the combined Phase 1/2 will be analyzed in FAS and EAS as described in item 3 and 5 of [Section 5.1](#) for subjects with R/R AML and overall subjects with different malignancy types. The demographics in the combined Phase 1/2 R/R AML subjects will be further summarized by refractory/relapse status in FAS.

Individual subject listings will be provided to support the summary tables.

8.1. Demographics

Age (years), height (cm), weight (kg), body mass index (BMI) (weight [kg]/height [m²]), body surface area (BSA), and other continuous baseline characteristics will be summarized descriptively (number of subjects, mean, SD, median, minimum and maximum). Age category (<60, 60 - <70, 70 - <75, ≥75 years), sex, race, and ethnicity and other categorical variables will be summarized by frequency tabulations (count, percent).

Age will be calculated as follows: age = Integer ≤ [(ICF date– Date of Birth + 1) / 365.25].

Body mass index will be calculated as follows: BMI (kg/m²) = weight in kg / (height in m)².

Body surface area will be calculated as follows: BSA (m²) = weight (kg)^{0.425} × height (cm)^{0.725}/139.2.

8.2. Baseline Disease Characteristics

The number and percentage of subjects in each of the following categories will be presented based on subject group structure described previously, when applicable. Continuous variables will be summarized using descriptive statistics (number of subjects, mean, SD, median, minimum, and maximum).

8.2.1. Baseline Disease Characteristics

1. ECOG PS at baseline (Grade 0, 1, 2, 3, or 4).
2. Gene mutation (IDH2) analysis at baseline (R140Q or R172K, or Unknown) (Local and Central).
3. UGT1A1 mutation status (heterozygous, homozygous, wild type, and NA).
4. R/R AML subtype (subjects who relapse after allogeneic transplantation; subjects in second or later relapse; subjects who are refractory to initial induction or re-induction treatment; subjects who relapse within 1 year of initial treatment, excluding subjects with favorable-risk status according to [National Comprehensive Cancer Network \[NCCN\] Guidelines \[NCCN v1.2015\]](#). Favorable-risk cytogenetics: inv(16), +(16;16),

t(8;21), t(15;17); subjects who have failed 2 or more cycles of first line therapy [consisting of an intermediate intensity chemotherapy, hypomethylating agent, or low dose cytarabine]).

5. Refractory/relapse status (primary refractory and relapse)
6. Prior systemic anti-cancer therapies for disease under investigation. (yes vs no).
7. Number of prior anti-cancer regimens (1, 2, 3, 4, and ≥ 5).
8. Prior stem cell transplants for AML (yes vs no); transplant type if yes (autologous, allogenic, other).
9. Cytogenetic risk status (favorable-risk, intermediate-risk, poor-risk, or failure).
10. Time (month) from last prior HSCT, calculated from starting date of prior HSCT to the first dose of AG-221.
11. Bone marrow blasts (%) and category (<20%; 20% to <30%; 30% to <50%; $\geq 50\%$) from the screening bone marrow aspirate/biopsy sample. Bone marrow aspirate will be used as the primary source. If no aspirate assessment is available, biopsy assessment will be used as default.
12. Peripheral blood blast (%).
13. Baseline values of the following lab parameters: Hemoglobin (<80 g/L, ≥ 80 g/L), platelet count (< $50 \times 10^9/L$, $\geq 50 \times 10^9/L$), absolute neutrophil count (ANC) (< $0.5 \times 10^9/L$, 0.5 to < $1 \times 10^9/L$, $\geq 1.0 \times 10^9/L$), white blood cells (WBC) (< $15 \times 10^9/L$, 15 to < $30 \times 10^9/L$, $\geq 30 \times 10^9/L$), creatinine clearance (<45 mL/min, 45 to <60 mL/min, ≥ 60 mL/min). These lab parameters will be summarized using descriptive statistics (number of subjects, mean, SD, median, minimum, and maximum) as well.
14. Number of red blood cell (RBC) transfusions and number of units transfused and number of platelet transfusions and number of units transfused. Transfusion occurred within 4 weeks prior to and 4 weeks after the first dose is defined as the baseline and will be summarized for Phase 1; and transfusion occurred within 8 weeks prior to the first dose will be summarized for Phase 2.

A by-subject listing of the above baseline disease characteristics will be provided.

